5.2.2. KNOWN POTENTIAL BENEFITS

The components of each study intervention have been independently shown to clinically improve pain intensity 10,14,18,24-28 and may improve other outcomes such as function or pain interference; however, neither improvement nor direct benefit is guaranteed to study participants. Study participants who improve on the treatment to which they are randomized will be allowed to continue that treatment either as a single treatment or augmented with an additional treatment. Participants who do not improve on the treatment to which they are randomized will be randomized to a new treatment. All study treatments will be provided free of charge to participants. Participants may also benefit by gaining new knowledge about their pain condition or by learning new pain self-management techniques. Participants may experience psychological benefit from interacting with study staff and personnel. Participation in the study may be beneficial to participants' general health, as participants might initiate and maintain healthy habits such as exercise. These benefits, if incurred, may be both immediate and long-term.

This research has the potential to benefit society in general by improving treatment for chronic low-back pain. Chronic low-back pain is a major cause of disability in the United States and causes both physical and emotional suffering. Patients are often unable to find adequate treatment for their condition, given the heterogeneity of patient phenotype including biomarkers, pain etiology and mechanism, and psychosocial characteristics. The goal of the study is to apply a precision medicine approach to chronic low-back pain treatment, which will allow more patients to receive the treatment that is likely to be best

for them. If providers are better able to target treatments, patients are likelier to improve. Long-term, this could reduce the prevalence of chronic low-back pain, improve pain and functional status, reduce the duration of symptoms, and reduce long-term opioid use.

5.2.3. ASSESSMENT AND MITIGATION OF POTENTIAL RISKS

Participant Understanding of Risks and Informed Consent

All participants enrolled in this study will provide informed consent based on an informed consent document that has been approved by the IRB of record for the study. The informed consent process will be administered by trained study staff and will include both verbal and written explanation of the study. This explanation will include describing the purpose of the study, phenotyping methods to be used, the time commitment required, all inclusion/exclusion criteria, potential risks and benefits, monetary and non-monetary compensation, study personnel contact information, and information on how study data and biospecimens will be shared within the BACPAC Consortium and with NIH approved repositories. All participants will be allowed to ask questions on any aspect of the protocol, and study personnel will provide answers and confirm there is no residual uncertainty regarding the study procedures prior to obtaining informed consent from the participant.

General Risk Mitigation Procedures

Protection of subjects from risk is multifaceted and includes monitoring the safety of the research participants, putting in place processes for minimizing research-associated risk, maintaining confidentiality of study data and participant identification, and reviewing and reporting adverse and unanticipated events.

Study staff at each site will be trained in HIPAA, CITI, and other human subjects research standards as required by site's institutional requirements. The Data Integration, Algorithm Development and Operations Management Center (DAC) will hold central training on study procedures and systems for clinical personnel prior to the start of the study and record these sessions for use by new staff members as needed during the study. If new procedures or forms are adopted during the study, additional training will be conducted via webinars. New clinical center staff will be trained by experienced staff at their site and through the training modules available via webinars. Each clinical site staff member will be certified on study procedures and systems, and certification records will be maintained at the sites for auditing. Each intervention arm will be delivered by appropriately trained and licensed personnel.

The measures taken to minimize risk associated with phenotypic assessments and study interventions are described below.

Risk Assessment & Mitigation for Phenotypic Assessments

Participants will be screened for contraindications to any of the BEST phenotyping procedures prior to enrolling in the study. All phenotyping activities (e.g., quantitative sensory testing, biomechanical assessments, blood draws) will be performed by appropriately trained and, where applicable, licensed personnel). Participating sites will be staffed by researchers with expertise in the assessment and treatment of chronic low-back pain, and the DAC will be responsible for ensuring all staff are trained and certified as required by the protocol prior to study launch.

Questionnaires: To minimize patient burden associated with completing a large number of questionnaires, as much as is feasible without sacrificing the validity of the data, participants will be

allowed to complete most questionnaires online prior to a scheduled visit or phone call assessment. This will allow participants to complete the questionnaires at their home or location of choice and to break up completion of the questionnaires into multiple sessions at their discretion. Participants will be instructed that they can contact study staff if at any point they become distressed while completing a questionnaire due to a lack of clarity about one or more questions or general discomfort caused by responding. While the completion of questionnaires will be incentivized, all participants will be told that they have the option to terminate participation without penalty and/or will be assisted in arranging medical/psychiatric help, if necessary.

Blood Draw / Venipuncture: In order to minimize risk of infection, venipuncture will be performed by trained medical personnel using aseptic technique including handwashing before and after the procedure and the utilization of sterile kits and gloves. Alcohol will be swabbed over the region of venipuncture prior to the procedure and a sterile bandage will be applied following the procedure.

Stool collection: Instructions regarding the safe collection of stool will be provided with each stool collection kit.

Biomechanical Assessment: Biomechanical assessments will be supervised by trained staff. Participants will be instructed that they can contact study staff if at any point they become distressed while completing an assessment.

Imaging: The primary established hazard associated with MR imaging is that the magnet exerts a strong force on metal objects. For this reason, metal objects are excluded from the vicinity of the magnet so that they will not become projectiles. In addition, each subject undergoes a standard screening procedure to determine whether they have any implanted materials that may pose a risk. If there is any doubt about the nature of any implanted material, the subject will not be scanned. Participants will be instructed to bring or wear clothing without metal fasteners and remove jewelry and any other metal objects from their body. Participants will wear foam earplugs or headphones to reduce the loud noises made by the scanner. Participants will be able to communicate with the examiner throughout the scan. If needed, the participant will be removed immediately from the scanner. MRI sessions will be conducted by trained personnel. Participants will be encouraged to contact the study team if they notice any unusual symptoms or untoward side effects. The investigators have extensive prior experience in the utilization of MRI for research. The MRI machine is operated within FDA guidelines so the potential for inducing peripheral nerve stimulation is low. Participants who report pregnancy will be excluded from MRI portion of the protocol.

Quantitative Sensory Testing (QST): Study personnel will be trained by the investigators to be sensitive to participant discomfort and concerns. Participants will be instructed that they can stop any QST procedure anytime that the pain or unpleasantness of the task becomes unbearable. All procedures have been thoroughly evaluated for reliability and safety, and are well tolerated by individuals with chronic pain, causing no more than temporary mild discomfort in the body regions that will be evaluated.

Genetic Analysis: Current federal law will help protect study participants from genetic discrimination in health insurance and employment.

Risk Assessment & Mitigation for Study Interventions

Participants will be screened for contraindications to any of the BEST study interventions prior to enrolling in the study. Participants who have a contraindication to a study intervention and who are

otherwise eligible for the study will be allowed to participate in the study but will not be randomized to the intervention for which they have a contraindication. In Sections 10.1 (Acceptance Commitment Therapy), 10.2 (Duloxetine), 10.3 (Enhanced Self Care), and 10.4 (Evidence-Based Exercise and Manual Therapy) specific details regarding risk assessment and mitigation are given for each study intervention.

Participants will be advised that they should contact study staff regarding any side effects or unexpected adverse events that occur while enrolled in the study. Prior to the start of a new study intervention, participants will be informed that if they are unable to tolerate the intervention, they are permitted to cease the intervention. Specifically for duloxetine, participants will be instructed on how to safely taper off the medication. In addition, study staff will conduct a phone call assessment with all participants approximately midway into each of the two intervention periods to evaluate pain-related outcomes as well as to ascertain how well the participant is tolerating their current study intervention(s). Participants who indicate they are unable to tolerate the intervention will be safely transitioned off their current intervention but, if in intervention period one, will be allowed to be randomized to a new intervention in the second study period. Additionally, all participants will be assessed for unexpected and adverse events 4 weeks after the end of the second intervention period (i.e., after completion of all study treatment).

Acceptance Commitment Therapy: Participants will interact with their therapist at least weekly, and the therapist will provide support as well as monitor for worsening of depression or anxiety symptoms including suicidal ideation. Participants will be encouraged to contact study staff with questions or concerns throughout the course of the study.

Duloxetine: Participants on duloxetine will be monitored appropriately for clinical worsening, suicidality, or unusual changes in behavior. Participants may be referred for appropriate treatment including emergency services if required. Participation can also be discontinued if there is active suicidal ideation.

Enhanced Self Care: The ESC intervention is an educational and self-care digital intervention. Risks are minimal; therefore, no intervention-specific risk mitigation is planned.

Evidence-Based Exercise and Manual Therapy: The EBEM intervention will be delivered by trained physical therapists or Doctors of Chiropractic. Participants who report local post-manipulation or exercise muscle and/or joint soreness will be instructed on appropriate self-care.

Run-in: The Run-in period is comprised of informational materials delivered digitally. Risks are minimal; therefore, no intervention-specific risk mitigation is planned.

Risk Assessment & Mitigation for Disclosure of Confidential Information

Several measures have been taken to minimize the risk of breach of confidentiality via unintended disclosure of confidential information. These include the general risk mitigation procedures described above (e.g., ensuring study staff have completed HIPAA, CITI, and other human subjects research training), providing highly secure electronic data collection systems and procedures (as described in Section 14), and collecting only essential identifiable information that is required for the study's scientific objectives and for critical operational reasons (e.g., contact information for scheduling study visits and conducting phone call assessments).

All reasonable steps will be taken to protect the privacy of participants. Each study participant will be assigned a unique study ID upon enrollment. All data and other artifacts collected for the study will be

identified by the participant's study ID. This includes data collected using the Carolina Data Acquisition and Reporting Tool (CDART) data management system, the online survey platforms, biospecimens, and web-based applications. Personally identifiable information will be segregated from other data. CDART implements a granular authorization model and enforces the principle of lease privilege access. Only a restricted set of authorized users will be allowed access to enter or view personal information. To further restrict data access, the CDART database is behind a network firewall which is open only to the CDART system itself.

The CDART data management system has robust security features including unique user logins with expiration dates and complex password requirements; storage of hashed passwords only; granular permissions based on user requirement to enforce the principle of least privilege access; and encrypted data transmission. The secure server environment where the systems that host CDART reside is located within a hardened data center on the UNC campus and is governed by standard UNC information security guidelines. Weekly vulnerability detection scans are performed using third-party vendor scanning tools, which include full administrative credentials to perform maximum detection techniques. Real-time virus protection software is implemented, and weekly full system virus scans are performed. Daily backups of the data are made and stored in an off-site location. CDART is 21 FDA Part 11 compliant.

5.2.4. RISK/BENEFIT JUSTIFICATION

The risks associated with phenotyping procedures are minimal. A greater understanding of the biomarkers, biomechanics, and etiology of chronic pain will improve future treatment recommendations and enhance quality of life for chronic low-back pain patients.

The risks associated with study procedures and interventions are generally minimal. The components of each of the study interventions have been previously studied and are in current clinical practice. There are well-studied side effects associated with duloxetine, but these side effects are generally mild to moderate for participants. Moreover, participants will be monitored for side effects and advised to discontinue if duloxetine is not well tolerated. These non-invasive treatments may reduce pain intensity, improve function, enhance self-management capacity, and increase psychological flexibility. Altogether, the potential benefit of these interventions outweighs the potential risk. The screening and monitoring of participants by study sites will ensure that risk remains low.

6. OBJECTIVES AND ENDPOINTS

The BEST Trial will inform a precision medicine approach to cLBP and is designed to identify treatments that are most effective in identifiable subgroups of patients. Therefore, the study was designed to estimate dynamic treatment regimes rather than to test the overall effectiveness of any single intervention or combination of interventions.

The primary objective is to estimate an algorithm to assign sequences of two cLBP treatments based on phenotypic markers and an individual patient's response to the initial treatment (*i.e.*, a dynamic treatment regime) that optimizes effectiveness.

In this trial, phenotypic markers will not be used to assign treatments, rather participants will be randomly assigned to treatment. Response to initial treatment will guide second-stage randomization and will be assessed with the Pain, Enjoyment of Life, and General Activity (PEG) scale and the Patient

Global Impression of Change (PGIC) 12 weeks after the first randomization. The primary analysis will then estimate an algorithm that can be applied to *cLBP* patients that will optimally assign treatments based on a patient's phenotypic markers and changing response (a dynamic treatment regime or DTR). Phenotypic markers that will be considered include, for example, preference for treatment and outcome priorities, history of depression, and time since diagnosis of chronic back pain. Study participant phenotypic markers will be assessed at baseline and a subset will be measured at the end of the first intervention period. As part of this analysis, we will compare the estimated best DTR that does *not* use phenotypic variables or participant response with the estimated *optimal* DTR. A hypothetical example of a DTR that we might estimate would involve a sequence of two decision rules: Individuals with chronic low-back pain receive physical therapy for 12 weeks and if pain intensity and interference are below a given threshold, continue regular follow up with patient; if pain interference is over the threshold, provide patient with prescription for duloxetine for 12 weeks.

This procedure will be applied to the following primary and secondary endpoints:

- Primary endpoint: 24-week change from baseline in patient-reported pain intensity and interference, measured with the Pain, Enjoyment of Life, and General Activity (PEG) scale at Visits 0 (baseline) and 2 (24 weeks of treatment)
- **24-week change from baseline in pain interference**, measured with the 4-item PROMIS Pain Interference scale (PROMIS-PI, 4a) at Visits 0 (baseline) and 2 (24 weeks of treatment)
- Incidence of opioid use, measured by self-report at Visit 2 (24 weeks of treatment)
- **24-week change from baseline in physical function**, measured with the PROMIS-PF Short Form 6b at Visits 0 (baseline) and 2 (24 weeks of treatment)
- 24-week change from baseline in depression score, measured with the PROMIS 4-item depression scale from the PROMIS 29 profile at Visits 0 (baseline) and 2 (24 weeks of treatment)
- **24-week change from baseline in anxiety score**, measured with the PROMIS Emotional Distress-Anxiety scale (PROMIS-EDA 4a) at Visits 0 (baseline) and 2 (24 weeks of treatment)
- **24-week change from baseline in sleep disturbance,** measured with the PROMIS short form 6a at Visits 0 (baseline) and 2 (24 weeks of treatment)
- **24-week change from baseline in sleep duration,** measured at Visits 0 (baseline) and 2 (24 weeks of treatment)

The PEG is a 3-item assessment of pain intensity and interference with enjoyment of life and general activity over the past week. This scale is validated, has low participant burden, is responsive to change, and captures multiple core outcome domains recommended by the Initiative on Methods, Measurement, and Pain Assessment in Clinical Trials (IMMPACT) and that are valued by people who experience chronic pain. ²⁹⁻³¹ In addition, pain intensity was considered the primary outcome of interest by the BACPAC Patient Advisory Board. Pain interference with be assessed using PROMIS-PI, which has demonstrated reliability and validity across diverse populations for the assessment of the degree to which pain interferes with physical, mental, and social activities. ³²⁻³⁴ Self-reported opioid use is included as a secondary endpoint. Additional secondary endpoints of physical function, depression, anxiety, and sleep disturbance are patient-centered and will be assessed using validated instruments from the PROMIS measure set. Depression and anxiety, common among individuals who experience chronic pain, negatively affect quality of life. ³⁵ Finally, PGIC is of key importance in the determination of response to treatment following the first randomization because it is valued by patients, integrates both positive and negative factors about treatment, and is responsive to change under pharmacologic and

nonpharmacologic treatment. It has been well validated,^{36,37} is reliable and is recommended as a global outcome measure for chronic pain by the IMMPACT.

The study has the following 3 secondary objectives:

Estimate DTRs that optimally balance multiple outcomes, taking into account participant preferences for outcomes including pain intensity, pain interference, physical function, opioid use, depression, anxiety, sleep duration and sleep disturbance.

Identification of DTRs that appropriately balance multiple outcomes will be accomplished by collecting participant preferences for outcomes at the two randomization points (Visit 0 and Visit 1) as well as overall satisfaction of the treatment at 12 and 24 weeks. This participant preference information will not be used to assign treatment during the study but will be used to estimate a participant-preference based DTR. The participant preference tool, CAPER, has been designed for use in this study and will be validated as part of its ongoing development in a BACPAC ancillary study.

Estimate DTRs that incorporate additional phenotypic markers (i.e., deep phenotyping) collected on a sub-set of participants.

A subset of participants (~n=200) will undergo 'deep' phenotyping that will include more comprehensive biomechanical assessments, functional brain imaging, and qualitative sensory testing. We will apply procedures discussed for the primary objective to estimate and identify DTRs to evaluate in future studies. While the precision of these estimates will be lower given the reduced sample size, we will learn what additional phenotypic measures may predict differential response to treatment.

Assess whether effectiveness is sustained on outcomes collected 24 weeks after randomization to the second treatment.

Endpoints will be the same as listed for the primary objective except that they will be measured at the final study visit (Visit 3) occurring 24 weeks after the second-stage randomization. Assessment of this aim will utilize procedures discussed for the primary objective.

The study has the following 3 exploratory objectives:

Evaluate the comparative effectiveness of individual treatments.

Evaluate the comparative effectiveness of different treatment regimes (i.e., a particular regime with a given set of rules at each decision point).

Evaluate the impact of treatment order on outcomes.

For these analyses we will estimate average treatment effects. Endpoints will include the primary and secondary endpoints identified in the primary objective, measured at 12 and 24 weeks after the first randomization.

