10.4.4. MEASURES TO MINIMIZE BIAS: RANDOMIZATION AND BLINDING

The **first-stage randomization** will use a randomized version⁶¹ of the Minimization method^{62,63} to maintain marginal covariate balance. Minimization is an alternative to stratified permuted block randomization for maintaining (marginal) covariate balance across treatments that is better equipped to handle a larger number of factors to balance on. When a participant is randomized, a measure of the marginal discrepancy between treatments is calculated and the patient is randomized using a biased coin method where whichever treatment would make the discrepancy smallest has a higher probability and the other treatments have equal, smaller probabilities. Covariates included in minimization algorithm:

[figure not shown]
- Willingness to participate in deep phenotyping (yes/no)
- Depressive or anxiety symptoms (yes/no)
- Duration of pain symptoms (<5 years/≥5 years)
- Current use of opioid treatment (yes/no)

A total of approximately 740 participants will be randomized to ACT (n=185), duloxetine (n=185), ESC (n=185), and EBEM (n=185) and which will require recruitment of approximately 820 participants, anticipating that 10% will not be randomized due to failure to meet eligibility criteria at the end of the run-in phase and an estimated 15% will be lost to follow-up over the course of the study. Participants who did not complete required run-in procedures will not be randomized. In order to assign equal numbers of participants to each of the 4 study interventions, randomization probabilities will account

for the fact that certain participants, e.g., because of a contraindication, may be eligible for only 3 of the 4 treatments.

Second-stage randomization will occur at the end of the first treatment period. Response to treatment will be assessed using the PEG and PGIC. Based on these scores, individuals will be grouped into 4 response classes.

- Group 1 participants (PGIC 1-2 and PEG <4) are assigned to maintain the first-line treatment.
- Group 2 participants (PGIC 1-2, PEG ≥4) are assigned to maintain the current treatment and augment with a randomly selected additional treatment.
- Group 3 participants (PGIC 3-4) are randomized to an **augmentation treatment or to switch** to a new treatment.
- Group 4 participants (PGIC 5-7) are randomly assigned to switch to a second-line treatment.

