^{*} Patients initially randomized to ESC with 12-week PGIC scores of 3-7 will be randomized to augmentation and not switching.

Table 10.1 provides a list of all possible augmentations (combinations of the initial treatment with a second study intervention) and treatment switches for each of the initial treatment assignments. This randomization will be performed within initial treatment by using the minimization method^{62,63} to achieve study-wide balance across treatments. Over the course of the study, the number and proportion of participants assigned to augmentation and switching overall, blinded to initial treatment assignment, will be monitored. If the proportions in each group differ meaningfully from the underlying assumptions used in the estimation of sample size, the proportion randomized to augment vs switch within Group 3 will be adapted to maintain power.

All Potential Second Stage All Potential Sw		All Potential Switches to Second
First Stage Treatment	Augmentations	Treatments
ESC	ESC + ACT	N/A
	ESC + Duloxetine	
	ESC + EBEM	
ACT	ESC + ACT	ESC
	ACT + Duloxetine	Duloxetine
	ACT + EBEM	EBEM
Duloxetine	ESC + Duloxetine	ESC
	ACT + Duloxetine	ACT

	Duloxetine + EBEM	EBEM
EBEM	ESC + EBEM	ESC
	ACT + EBEM	ACT
	Duloxetine + EBEM	Duloxetine

Participants who must discontinue first-stage treatment early, regardless of their PGIC or PEG score, will be randomized to switch to a second treatment. These individuals will discontinue treatment and will be randomized to switch to a second-line treatment 12 weeks post baseline (Visit 1).

Randomization will be performed using the Carolina Data Acquisition and Reporting Tool (CDART), developed by the Collaborative Studies Coordinating Center at the University of North Carolina. CDART is designed and implemented as a centrally hosted, web-based, customizable and scalable data management system. Randomization algorithms will be developed by a biostatistician and custom-written in Java, which provides a full set of libraries and tools capable of complex algorithm implementation. This data management system will provide a means for implementing treatment allocation protocols, masking allocation of future participants, and for study staff to obtain allocation information immediately following randomization. Study staff and participants will not be blinded to treatment allocation given the nature of the interventions. Study investigators and staff involved in data analysis will be blinded to assignment.

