We can test the null hypothesis that the value of two different DTRs are equal. Let \mathbf{d}^0 denote the best DTR that does not consider a participant's phenotype (the best zero-order DTR). This DTR assigns every participant the treatment with the best population average treatment effect. Let \mathbf{d}^{opt} denote the optimal DTR that considers participant phenotype. We can conduct two-sided tests of superiority of the hypothesis

$$H_0$$
: $\mathbf{V}(\mathbf{d}^0) = \mathbf{V}(\mathbf{d}^{\text{opt}})$
 H_1 : $\mathbf{V}(\mathbf{d}^0) \neq \mathbf{V}(\mathbf{d}^{\text{opt}})$

For the other interventions that are not the best, we can analogously define a DTR that always recommends each of these treatments and compare them to each other and to the optimal DTR.

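### The planned benchmark for the optimal regime ignores Week 12 response, but Stage 2 options are set by response class, so none of the 25 response-blind sequences is supported in all four classes and the extrapolation needed is not stated

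*Protocol*

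**What the plan says.** Protocol Section 6 (Objectives and Endpoints) says that the primary analysis will include a comparison of the best DTR that does not use "phenotypic variables or participant response with the estimated" optimal one. Section 13.1 formalises the comparator under the exploratory objectives. It introduces it as a regime that ignores phenotype and then makes it static: "This DTR assigns every participant the treatment with the best population average treatment effect". For the remaining interventions it says one can "analogously define a DTR that always recommends each of these treatments and compare them to each other and to the optimal DTR". Section 13.2 gives values for regimes of this kind: each treatment in both stages, and EBEM followed by duloxetine plus EBEM for everyone.

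Section 10.4.4 sets the Stage 2 rules:

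- The best responders have no alternative: "Group 1 participants (PGIC 1-2 and PEG <4) are assigned to maintain the first-line treatment".
- Group 2 (improved on PGIC, but PEG still 4 or more) keeps its treatment and adds one chosen at random; it can neither stay on one treatment nor switch.
- Group 3 (PGIC 3-4) is the only class randomized between action types, either adding a treatment or changing to another.
- The poorest responders can only change treatment: "Group 4 participants (PGIC 5-7) are randomly assigned to switch to a second-line treatment".
- ESC starters are an exception, because the table lists no switch for them: "Patients initially randomized to ESC with 12-week PGIC scores of 3-7 will be randomized to augmentation and not switching". Section 7.1 agrees: they maintain in Group 1 and otherwise augment.

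Participants who must stop first-stage treatment early are switched whatever their scores (Section 10.4.4). The SAP places the value of the estimated optimal DTR outside its scope (Multiplicity Adjustments).

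**The concern.** A regime that ignores response applies one Stage 2 action to every participant who started on a given treatment. To value it from the randomization, that action must have been possible in every response class. Here the class decides whether a participant may maintain, augment or switch, and only Group 3 is randomized between action types. For any response-blind regime there is therefore at least one class in which nobody was assigned the action. The fitted Q-functions must fill that gap, and the answer depends on whether the effect of a Stage 2 option is allowed to differ by Week 12 response. The trial cannot check this where the option was never given.

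At stake is how the comparison is read. A difference between the optimal regime and this benchmark would look like a randomized contrast, while part of the benchmark's value comes from a modelling assumption that nobody has written down.

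**Working it through.** **Step 1. Reproduce the protocol's benchmark values (Section 13.2).** Take the printed Stage 2 model without its prognostic terms, as the protocol's tables do, and read the ACT-EBEM interaction coefficient as -0.1, which the protocol's own 0.85 requires (0.25 + 0.40 + 0.30 - 0.10).

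- Optimal rule: at X1 = -1, ACT + duloxetine = 0.25 + 0.30 - 0.10 = 0.45. At X1 = 1, duloxetine + EBEM = 0.30 + 0.40 + 0.30 - 0.10 = 0.90. Mean (0.45 + 0.90)/2 = 0.675.
- Best static rule, duloxetine + EBEM for everyone: at X1 = -1, 0.30 + 0.40 - 0.30 - 0.10 = 0.30; at X1 = 1, 0.90. Mean (0.30 + 0.90)/2 = 0.60.

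Both match the protocol (0.675 and 0.6; ratio 0.60/0.675 = 0.889). The protocol's comparator is thus a fixed action for everyone.

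**Step 2. List the static sequences (Table 10.1 plus maintenance).** ESC first: 1 maintain + 3 augment = 4. ACT, duloxetine or EBEM first: 1 maintain + 3 augment + 3 switch = 7 each, so 3 × 7 = 21. Total 4 + 21 = 25.

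**Step 3. Find the classes in which each has positive probability.**

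| Sequence type | Number | Supported in | Unsupported share |
|---|---|---|---|
| Maintain ('always k') | 4 | Group 1 | 1 - p1 |
| Non-ESC augment | 9 | Groups 2, 3 | p1 + p4 |
| Non-ESC switch | 9 | Groups 3, 4 | p1 + p2 |
| ESC augment | 3 | Groups 2, 3, 4 | p1 |

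Here p1 to p4 are the class shares among those who started on the treatment in question. Supported in all four classes: 0 of 25. The protocol's best static regime, EBEM then duloxetine + EBEM, can be observed only in Groups 2 and 3. This result needs no class shares, only that each class contains someone. The SAP's cutoff (PEG at or below 4 against above 4) differs from the protocol's (below 4 against 4 or more) but does not change it.

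**Step 4. Size of the gap.** The documents give no class shares. Three assumed splits for Groups 1/2/3/4 show the range:

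| Assumed split (%) | 'Always k' | Non-ESC augment | Non-ESC switch | ESC augment |
|---|---|---|---|---|
| 10/10/50/30 | 90% | 40% | 20% | 10% |
| 20/15/45/20 | 80% | 40% | 35% | 20% |
| 30/20/40/10 | 70% | 40% | 50% | 30% |

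The constant 40% arises because p1 + p4 happens to be 40% in all three splits. 'Always k' has a larger gap than augmentation whenever p1 is below p2 + p3, and ESC augmentation never has a larger gap than non-ESC augmentation or switching.

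With no modelling assumption, the mean Week 24 PEG (0-10) in an unsupported class could lie anywhere on the scale, so bounds on the regime mean are 10 × the unsupported share wide: 10 × 0.40 = 4 points for EBEM then duloxetine + EBEM, 1 to 3 points for ESC then augmentation, and 7 to 9 points for 'always k'.

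**Step 5. Count the marker-free regimes that the design does support.** These take a first treatment and one allowed option per class. Non-ESC: 1 × 3 × 6 × 3 = 54 each, 3 × 54 = 162. ESC: 1 × 3 × 3 × 3 = 27. Total 162 + 27 = 189, for a participant eligible for all four treatments and with early discontinuers placed in Group 4.

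**The case against.** Several points on the other side stand.

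- **Weight of the contrast.** A reader might infer that the primary result rests on it. It does not. Section 13.1 names the DTR's parameters and its value as the primary estimation targets. The sample size rests on the ratio of the estimated regime's value to the optimal value, with no role for the benchmark. The formal test and the 'always k' regimes are exploratory and worded as things that can be done. Section 6 nevertheless commits to the comparison within the primary analysis.
- **Can it be estimated?** A reader might infer that no estimate is possible. Q-learning is regression and will return a number for a static regime, for example from a model with no interaction between response and Stage 2 treatment. What is missing is a statement of that assumption and a check of sensitivity to it.
- **Size.** A reader might infer that the benchmark rests on actions most participants could never receive. Under the assumed splits that fits 'always k', but not non-ESC augmentation (40%) or ESC augmentation (10-30%).
- **Mixing response and markers.** A reader might fault the contrast for combining gain from reacting to response with gain from markers. Section 6 drops both from the comparator openly, so it targets the total gain from tailoring. That is a legitimate question, although it does not isolate markers.
- **Related plans.** Sections 6 and 13.4.1 already plan comparisons of regimes with given rules and of embedded regimes. The protocol defers detail to a SAP, the SAP supplied excludes the DTR analysis, and its reference list includes a separate statistical design paper that is not available here. Whether allowed sets are defined there is unknown. Neither document supplied defines them for this comparison.

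**Conclusion.** The point holds as one about identification and specification. No static two-stage sequence (0 of 25) has positive probability in all four response classes. The Section 6 comparator, the static comparator of Section 13.1 and the 'always k' regimes therefore need extrapolation that neither document states. The count follows from the assignment rules alone. The size of the gap does not: the percentages and the PEG bounds rest on assumed class shares.

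Two qualifications. Early discontinuers switch whatever their scores, but that gives no support for switching among other participants in Groups 1 and 2. A first treatment followed by the trial's own class-based assignment is supported, and the SAP's Stage 1 least squares means describe it, but it uses response and so is not the Section 6 comparator.

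The documents do not support a conclusion that the primary objective, the randomization, the sample size or the SAP's Week 24 means are undermined. The change should be made before the DTR comparison is run.

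**What to change.** 1. In Sections 6 and 13.1, define the comparator as the best marker-free embedded regime: a first treatment plus one allowed Stage 2 option in each response class (162 + 27 = 189 candidates, fewer for participants contraindicated to one treatment).
2. State how early discontinuers enter. The SAP (Trial/Study Design) groups those who could not tolerate treatment with PGIC 5-7, which keeps the count at 189. The switch rule for early discontinuers in Section 10.4.4 conflicts with the absence of any switch for ESC starters in the same section and Table 10.1; these passages must be reconciled.
3. Replace 'always k' with 'start with k, then the best allowed marker-free option per class'.
4. Restrict the estimated optimal DTR to the same allowed sets. Section 13.1 defines it over all treatment pairs, and the illustrative optimum in Section 13.2 gives ACT + duloxetine after any first treatment, a pair absent from the ESC and EBEM rows of Table 10.1. With both regimes restricted, the contrast measures what phenotypic markers add beyond response.
5. If the total gain over a static regime is still wanted, report it as a secondary, model-dependent estimate, with the extrapolation assumption written out and a sensitivity analysis that lets Stage 2 effects differ by response class.

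The cost is wording in Sections 6 and 13.1, the corresponding text in whatever plan governs the DTR analysis, and analysis code. No new data are needed.
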